Table 3 Medications and Procedures.	38
TABLE OF FIGURES	
Figure 1 Study Schematic	29

List of Abbreviations and Definitions of Terms

_	and Definitions of Terms			
ADR	Adverse Drug Reaction			
AE	Adverse Event			
AMT	Amniotic Membrane Transfer			
AT	Artificial Tears			
BCDVA	Best Corrected Distance Visual Acuity			
BLA	Biologics License Agreement			
°C	Degrees Celsius			
CFR	Code of Federal Regulations			
CRA	Clinical Research Associate			
CRF	Case Report Form			
CRO	Contract Research Organization			
DHHS	Department of Health and Human Services			
DSUR	Development Safety Update Report			
EC	Ethics Committee			
e-CRF/CRF	Electronic/Case Report Form			
EDC	Electronic Data Capture			
ETDRS	Early Treatment Diabetic Retinopathy Study			
EU	European Union			
°F	Degrees Fahrenheit			
FCS	Fluorescein Corneal Staining			
FDA	Food and Drug Administration			
GCP	Good Clinical Practice			
GVHD	Graft Versus Host Disease			
HIPAA	Health Insurance Portability and Accountability Act			
ICF	Informed Consent Form			
ICH	International Conference on Harmonisation			
IDEEL	Impact of Dry Eye on Everyday Life			
IEC	Independent Ethics Committee			
IND	Investigational New Drug			
IRB	Institutional Review Board			
LNGFR	Low-Affinity Nerve Growth Factor Receptor			
Log MAR	Logarithm of the Minimum Angle of Resolution			
mg/ml	Milligrams per millilitre			
MGD	Meibomian Gland Disease			
ml	millilitre			
mNGF	Murine Nerve Growth Factor			
MOP	Manual of Procedures			
NEI	National Eye Institute			
NGF	Nerve Growth Factor			
NGF0212	Phase II Randomized, Double-Masked, Vehicle-Controlled Trial of			
(REPARO)	Recombinant Human Nerve Growth Factor for			
	·			

	Neurotrophic Keratitis (REPARO)
NGF0214 (US Trial)	Topical Recombinant Human Nerve Growth Factor (Cenegermin) for Neurotrophic Keratopathy Multicenter Randomized Vehicle-Controlled Pivotal Trial
NK	Neurotrophic Keratitis/Keratopathy
OCP	Ocular Cicatricial Pemphigoid
OCT	Optical Coherence Tomography
PED	Persistent Epithelial Defect
PID	Patient Identification``
PI	Principal Investigator
PK	Punctate keratitis
rhNGF	Recombinant Human Nerve Growth Factor
SAE	Serious Adverse Event
SLE	Slit Lamp Examination
SUSAR	Suspected Unexpected Serious Adverse Reaction
SPK	Superficial punctate keratitis/keratopathy
TEAE	Treat-Emergent Adverse Events
TFBUT	Tear Film Break Up Time
μl	Microliter
μg/ml	Microgram per millilitre

1. STUDY SYNOPSIS

CLINICAL STUDY SYNOPSI	S:				
Study Number	NGF0120				
Title of Study	An 8-week, multicenter, open label, prospective study with 24 weeks of follow-up to evaluate safety and efficacy of OXERVATE™ 0.002% (20 mcg/mL) cenegermin-bkbj ophthalmic solution in patients with Stage 1 Neurotrophic Keratitis (NK)				
Short Title	DEFENDO				
EudraCT N°/IND	115892				
Study Centers (Country)	Approximately 5 US study centers				
Development Phase	IV				
Objectives	Primary Objective The primary objective of this study is to evaluate the safety and efficacy of OXERVATE™ 0.002% (20 mcg/mL) cenegermin-bkbj ophthalmic solution administered 6 times daily for 8 weeks on the ocular surface, visual function and quality of life in patients with Stage 1 NK. Secondary Objective The secondary objective is to evaluate patients who heal at week eight and remain healed (as defined in section 3.3) throughout the follow-up period. In addition, the study aims to evaluate the percentage of subjects that achieve an improvement in corneal sensitivity as measured by the Cochet-Bonnet aesthesiometer at 4 and 8 weeks, and by the last visit week 32. Exploratory Objectives The exploratory objectives are to evaluate the change from baseline to weeks 4 & 8 in Schirmer I and the Tear Film Break-Up Time (TFBUT). Additional Objectives (site specific) The additional objectives are to evaluate the change from baseline at week 8 and week 24 in confocal microscopy and anterior segment Optical Coherence Tomography (OCT).				

This clinical study will be a multi-center, open label, prospective study of 8 weeks of treatment with 24 weeks of follow-up to evaluate the safety and efficacy of OXERVATE 0.002% (20 mcg/mL) cenegermin-bkbj ophthalmic solution administered as one drop in the affected eye(s), 6 times per day at 2-hour intervals, for eight weeks in patients with Stage 1 Neurotrophic Keratitis (NK). The study is divided into four phases as follows:

- 1. Screening Visit (Day -14): Procedures for inclusion will be performed at both Visit 1 (Screening) and Visit 2 (Baseline). Commercially available artificial tears (AT) provided by the sponsor will be permitted during the Screening period as needed up to four times a day.
- 2. Washout period (from day minus 14 to day 0): 14 days with no further treatment except commercially available preservative-free artificial tears provided by the sponsor (Note: Xiidra[™] and Restasis[™] use is disallowed for 14 days prior to Visit 2.) Artificial tears (AT) provided by the sponsor will be permitted up to four times a day and will be tracked via daily diary during washout period.

3. **Treatment:**

- a. Treatment (weeks 1-8): eligible patients will start OXERVATETM 0.002% (20 mcg/mL) cenegermin-bkbj ophthalmic solution administered as one drop in the affected eye(s), 6 times per day at 2-hour intervals, for eight weeks. During the treatment period, only study product will be permitted for topical ocular treatment.

 Commercially available preservative free artificial tears (AT) provided by Sponsor are not allowed during the treatment period except as rescue therapy.
- 4. Follow up (weeks 9-32): For the 24 weeks post treatment:
 - a. For patients completely healed, no treatment is allowed except for commercially available AT provided by the Sponsor, administration frequency is at the physician's discretion during follow-up based on patients need for

Study Design and Methodology

- lubrication. The use of artificial tears will be tracked via a daily dosing diary.
- b. For patients not completely healed and who don't meet criteria for premature discontinuation, will also be followed up but any topical treatment is allowed at the discretion of the physician. All treatments will be tracked as concomitant medications. No surgical procedures are permitted during the follow-up (i.e. sutured Amniotic Membrane Transfer (AMT), sutured tarsorrhaphy). Permitted items include topical medications and suture less AMT.

The study will be a total of 34 weeks in duration: a screening period of 2 weeks, followed by 8 weeks of treatment and a 24-week follow-up period. At the end of the screening period (at Visit 2), patients meeting the entry criteria for this study will be assigned to treatment with OXERVATE[™] 0.002% (20 mcg/mL) cenegermin-bkbj ophthalmic solution which will be known as Study Product beginning the morning following Visit 2.

Following the completion of the treatment period, patients will be followed up for an additional 24 weeks (for patients healed and non-healed [and not meeting discontinuation criteria] at Week 8) and will be evaluated at the end of the follow-up period. At the investigator's discretion, the subject may be seen for an Unscheduled Visit to evaluate for safety. Patients who prematurely discontinue for whatever reason will not be followed post discontinuation and should have Visit 6 assessments completed.

At Visit 1, eligible patients will be instructed to discontinue all topical ophthalmic medications and will only be allowed to use commercially available preservative-free artificial tears provided by the sponsor to be used up to four times per day during the screening period. At the conclusion of the Baseline Visit (Visit 2) eligible patients will be dispensed a 2-week supply of Study Product from the onsite freezer in a sealed bag and will be instructed to self-administer the Study Product one drop six times a day starting on the day after Day 0/ Visit 2 through Week 8 of the controlled treatment period.

A two week supply of study product will additionally be dispensed to the patients during the treatment period at Visits 3, 4 and 5/Weeks 2, 4 and 6.

Starting from Visit 2, only the study product will be allowed. Preservative free AT provided by the sponsor *will not* be used during the study product treatment period. After the 8 weeks of study product treatment, and during the follow up period, AT should be used only if strictly needed. The use of AT will be tracked in the daily dosing diary.

At Visit 6 (End of Treatment), patients will be assessed for corneal healing.

Rescue Therapy: Commercially available preservative free artificial tears (AT) provided by Sponsor are not allowed during the treatment period. Per the investigators discretion if the patient requires rescue therapy during the 8-week treatment period then they can receive artificial tears provided by the sponsor up to four times per day. The frequency of rescue therapy must be documented in the patient's diary.

Completely healed patients at week 8 are defined by SPK as Grade ≤1 in the central qualifying zone via FCS (per NEI scale) and no persistent staining in the non-qualifying zones (excluding the superior zone) defined as the absence of pathological staining via corneal photography. Patients who are completely healed at Week 8 will be followed for an additional 24 weeks during the follow-up period. During the 24-week follow-up period (Weeks 9-32) the patients will be followed without any Study Product, however, preservative-free AT (provided by the study sponsor) may be used and documented on the daily diary. If warranted for patient safety, the Investigator may elect to see the subject at an Unscheduled Visit(s) to evaluate the patient.

Patients who are not completely healed at week 8 defined by SPK as Grade 2 via FCS in the central qualifying zone AND who do not meet the criteria for premature discontinuation, will also be followed for an additional 24 weeks during the follow-up period. During the 24-week follow-up period (Weeks 9-32) the patients will be followed and may be treated at the physician's discretion (retreatment

with OXERVATE[™] 0.002% (20 mcg/mL) cenegerminbkbj ophthalmic solution is not permitted). Any concomitant treatment must be documented on concomitant medication log. If warranted for patient safety, the Investigator may elect to see the subject at an Unscheduled Visit(s) to evaluate the patient.

Patients who meet the definition of Deterioration or No Improvement in the study eye at week 8 and during the follow up period, will be discontinued from the study and treated as appropriate at the discretion of the investigator. Deterioration or No Improvement is defined by any of the following:

[figure not shown]
- In the Study Eye, the FCS is unchanged (Grade=3) from baseline in the qualifying NEI zone.
- At the PIs discretion in the study eye if any of the non-qualifying zones progress from baseline.
- decrease in BCDVA by >10 ETDRS letters from baseline.
- progression in staining to a lesion/PED or corneal melting or perforation.
- onset of infection (viral, fungal, bacterial)
- Require an ocular surgical procedure, including the need for a corneal transplant.

Note: If there is a deterioration in the non-study eye, the Investigator may discontinue treatment in that eye and initiate alternative treatment at their discretion in the non-study eye but continue following the study eye per protocol.

All patients will attend the following clinic visits in the following sequence:

- Screening (Visit 1/Day -14)
- Baseline and First Study Product Pick-Up (Visit 2/Day 0)
- Product Pick-Up (Visit 3/Week 2)
- Treatment Assessment and Study Product Pick-Up (Visit 4/Week 4)
- Product Pick-Up (Visit 5/Week 6)
- End of 8-week Treatment (Visit 6/Week 8)
- Follow-Up and Final Study Visit (Visit 7/Week 32)

- 6. The same eye (eligible eye/study eye) fulfills all the above criteria on the day of Screening (Visit 1) and again on Visit 2.
- 7. Patients with punctal occlusion or punctal plugs inserted prior to the study are eligible for enrollment provided that the punctal occlusion is maintained during the study period. If a punctal plug falls out during the study, it must be reinserted within 7 days.
- 8. Patients who are at high risk of progression or have a history of Stage 2 or Stage 3 NK per the Mackie classification.
- 9. Patients who have only one functional eye can be included if they meet all the criteria above and per the investigator's discretion are proper candidates to designate the one functional eye as the study eye.
- 10. Only patients who satisfy all Informed Consent requirements may be included in the study. The subject and/or his/her legal representative has read, signed, and dated the IRB approved Informed Consent document before any study-related procedures are performed.
- 11. Patients must have the ability and willingness to comply with study procedures.

Exclusion Criteria:

- 1. In the opinion of the Investigator, there is evidence of an active ocular infection (bacterial, viral, protozoal) in either eye.
- 2. Use of non-diagnostic (e.g., topical drops used for clinical testing/evaluations) medications that can induce corneal toxicity between Visit 1 and Visit 2.
- 3. In the opinion of the investigator, have current or history of conditions that may confound the study data including but not limited to Ocular Cicatricial Pemphigoid (OCP), Graft Versus Host Disease (GVHD), neuromyelitis optica, uncontrolled dry eye, and Steven Johnson's syndrome.
- 4. History of severe systemic allergy or severe ocular allergy (including seasonal conjunctivitis expected during the subject's participation in the trial) or chronic conjunctivitis and/or keratitis other than dry eye disease.

- 5. Intraocular inflammation defined as Tyndall score >0.
- 6. Patients with severe vision loss with no potential for visual improvement in the study eye, in the opinion of the investigator, or if the subject is deemed legally blind.
- 7. Patients with active severe blepharitis and/or severe meibomian gland disease who in the opinion of the investigator will require routine treatment during the study or have required routine treatment within 2 weeks of the study treatment visit (Visit 2). (This includes the use of doxycycline within 2 weeks prior to the treatment visit (Visit 2) for active MGD.)
- 8. History of any ocular surgery (including eyelid surgery and cataract surgery) within the three months before study treatment (Visit 2) and for Lasik or refractive surgical procedures within 3 months before study treatment (Visit 2). (An exception to the preceding statement is allowed if, in the opinion of the investigator, the ocular surgery is deemed the cause of the NK.)
- 9. Ocular surgery or elective ocular surgery expected during participation in the trial.
- 10. Prior surgical procedure(s) for the treatment of NK including but not limited to tarsorrhaphy, conjunctival flap, the exception is for amniotic membrane transplantation. Enrollment of patients previously treated with amniotic membrane transplantation is allowed two weeks after the membrane has fully disappeared within the area with removal of any sutures or two weeks from removal of the Prokera ring before study treatment visit (Visit 2).
- 11. Treatment with Botox (botulinum toxin) injections in the study eye, used to induce pharmacologic blepharoptosis within 60 days prior study treatment visit (Visit 2).
- 12. Anticipated need to use therapeutic contact lenses or contact lens wear for refractive correction during the study treatment period in the Study Eye.
- 13. Patients with unstable medical condition that may confound the study data in the opinion of the investigator including but not limited to diabetes, thyroid disease, autoimmune disease, Parkinson's disease, and Multiple Sclerosis. Stable conditions

- managed with oral or injectable medications can be included, if per the investigator's discretion the patient is not anticipated to have flare ups that could affect the ocular surface.
- 14. Patients with eyelid abnormality that may alter eyelid function including but not limited to Blepharospasm, Cerebrovascular accident, entropion, ectropion, floppy lid syndrome.
- 15. Use of glaucoma drops within 14 days prior to study treatment visit (Visit 2) and for the duration of the study. Patients can use oral Diamox during the study to control IOP.
- 16. Pregnant or lactating at study entry or who are planning a pregnancy.
- 17. Premenopausal female not using a medically acceptable form of birth control (abstinence, oral contraception, intrauterine device, surgically sterilized).
- 18. History of drug addiction or alcohol abuse documented within the past 5 years.
- 19. Participation in a clinical trial with a new active substance 14 days prior to study treatment visit (Visit 2). Per the investigator's evaluation that the participation in another clinical trial for an ocular surface product does not have residual effects on the ocular surface beyond 14 days prior to treatment that could confound the data by having an effect on staining.
- 20. Participation in another clinical trial study at the same time as the present study.
- 21. Participation in a Neurotrophic Keratitis study during the past 60 days prior to study treatment visit (Visit 2).
- 22. Are an employee of the site that is directly involved in the management, administration, or support of this study or be an immediate family member of the same.
- 23. Prior failure with treatment for Stage 1, 2 or 3 NK with OXERVATE[™] 0.002% (20 mcg/mL) cenegermin-bkbj ophthalmic solution. Failure defined as non-responder or lack of efficacy.

Study Product, Dosage and Mode of Administration	 OXERVATE[™] 0.002% (20 mcg/mL) cenegermin-bkbj ophthalmic solution: in a multiple-dose vial 6 times/day Topical Drop
Duration of Treatment	8 weeks
Reference product, Dosage and Mode of Administration	NA
Efficacy Endpoints	 Percentage of patients who experience epithelial healing at 4 and 8 weeks. (Epithelial healing is defined as Grade 1 or absence of staining (Grade 0) in a previously qualifying zone.) Percentage of patients who remain healed (as defined in #1 above) throughout the follow-up period. Schirmer I change from baseline to weeks 4 & 8 TFBUT change from baseline to weeks 4 & 8 Percentage of patients that achieve an improvement in corneal sensitivity in the NEI zone used to qualify in the study eye as measured by the Cochet-Bonnet aesthesiometer at 4 and 8 weeks, and at the last visit (week 32). Mean change in BCDVA from baseline to Week 8. Percentage of patients that achieve a 15- letter gain in BCDVA at 4 and 8 weeks. Quality of life questionnaires change from baseline at week 8 and week 32 IDEEL EQ-5D-5L.
Exploratory Efficacy Endpoints	 Frequency of preservative free artificial tears use (n° drops/day) during the follow up period. At selected sites: The following may be evaluated as part of a post-hoc analysis: Change from baseline structural nerve regeneration (density, length, nerve density, tortuosity) per confocal microscopy. Change from baseline in epithelial thickness per anterior segment OCT.

Safety Measures	Adverse Event Monitoring
Safety Measures Statistical Methods	Subject Characteristics and Disposition: For categorical variables, frequencies and percentages will be presented. Continuous variables will be summarized using descriptive statistics (n, mean, median, standard deviation, minimum, and maximum). Baseline demographic and background variables will be summarized. The number of patients who enroll in the study and the number and percentage of patients who complete the study will be presented. The frequency and percentage of patients who withdraw or discontinue from the study, along with the reason for withdrawal or discontinuation, will also be
	with the reason for withdrawal or discontinuation, will also be summarized. Analysis of efficacy variables: Analyses for responder outcomes will include percentage of response and exact 95% confidence intervals. Analyses of change from baseline and continuous outcomes will include mean and associated asymptotic 95% confidence intervals. No formal hypothesis test will be conducted.
	Analysis of safety variables: Adverse events (AEs) will be coded by preferred term and system organ class using the latest version of the Medical Dictionary for Regulatory Activities and will be summarized overall. AEs will also be summarized by severity and relationship to study drug. Serious AEs and AEs leading to discontinuation of study drug will also be summarized.

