6.2. EARLY WITHDRAWAL FROM STUDY

A premature discontinuation will occur when a patient who signed the ICF ceases participation in the study, regardless of circumstances, before the completion of the study protocol procedures. Patients can be prematurely discontinued from the study for one of the following reasons:

- Progression from Stage 1 to Stage 2 or Stage 3 NK, or corneal melting/perforation
- At the PI discretion patient is considered to be a non-responder (no improvement from baseline).
- In the qualifying/Study Eye, the FCS is unchanged (Grade=3) from baseline after 8 weeks of treatment in the qualifying NEI zone or there is an increase in FCS ≥1 within a non-qualifying NEI zone in the same eye.
- Decrease in BCDVA by >10 ETDRS letters
- Onset of infection (bacterial or viral)
- Protocol violation, including lack of compliance defined as <80% of doses taken based on diary documentation between treatment clinic visits.
- Withdrawal of consent
- Lost to follow-up during the treatment period (Every effort must be made to contact the patient; a registered letter must be sent)
- Study terminated by the Sponsor
- Other reasons, such as administrative reasons or pregnancy
- Development of AE or unacceptable toxicity per the investigator's discretion, precluding further therapy with the study drug.
- Severe protocol violations, such as an incorrect treatment administration, or a concomitant use of not permitted medications. Before removal, these cases should first be discussed with Dompé.

The reasons for premature discontinuation from the study will be reflected on the Study Termination Record of the CRF. For patients who prematurely discontinue, Visit 6 procedures will be completed, and these patients will be considered off study and will no longer be followed.

For patients that discontinue prematurely, the investigator should refer patients for further treatment as appropriate.

Replacement Procedures

Patients in this study who prematurely discontinue before completion of 8 weeks of treatment with OxervateTM will be replaced. Patients prematurely discontinuing during follow up treatment will not be replaced.

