9.1. SAMPLE SIZE

A sample size of 35 evaluable patients (patients completing 8 weeks of OxervateTM) will achieve a lower limit of 95% confidence interval equal to 40% and 54% when the percentage of subjects who experience epithelial healing is 58% (at 4-week) and 72% (at 8-week), respectively.

The sample size calculation was based on previous trial calculations from NGF0212 (REPARO) and NGF0214 (US trial) that showed statistical superiority in complete healing after 8 weeks of treatment with cenegermin, 72% and 65.5% respectively. Assumption for this target, has been proportion of patients achieving complete healing of staining (grade 1 or less on NEI scale) by week 8.

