5 ANALYSIS OF EFFICACY

5.1 Primary Efficacy Variable

The primary efficacy variable is the achievement of epithelial healing at Visit 6/Week 8, which is defined as Grade 1 or absence of staining (Grade 0) in the central qualifying zone of study eye via FCS (per NEI scale). The primary efficacy variable will be summarized as a binary goal attainment variable (Yes/No).

The primary analysis will be based on observed cases (i.e. no missing data imputation). As a sensitivity analysis, the last post baseline observation prior to Week 8 will be carried forward for imputing missing data at Week 8. In addition the worst post baseline observation prior to Week 8 will be carried forward for imputing missing data at Week 8 and patients who took any rescue medication prior to Week 8 will be considered as a treatment failure (not epithelial healed) at Week 8.

All summaries and analyses for the primary efficacy variable will be presented for both FAS and FTS populations.

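### The Week 8 healing rate rests on central staining alone, and no planned analysis shows how far it depends on eyes that received prohibited treatment or met a deterioration criterion

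*Protocol*

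**What the plan says.** **Endpoint.** SAP 5.1 names epithelial healing of the study eye at Visit 6/Week 8 as the primary variable, "which is defined as Grade 1 or absence of staining (Grade 0) in the central qualifying zone of study eye via FCS". The primary analysis uses observed cases and is shown for the FAS and the Full Treated Set (FTS).

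**Deterioration.** The protocol synopsis and section 3.3 provide for the discontinuation of "Patients who meet the definition of Deterioration or No Improvement in the study eye at week 8". They list the grounds on which a study eye is classed as deteriorated or not improved, among them a BCDVA loss of more than 10 letters, onset of infection, and "Require an ocular surgical procedure, including the need for a corneal transplant". Protocol 6.2 adds severe violations, including "a concomitant use of not permitted medications", as a possible reason for discontinuation, to be discussed with the sponsor before removal.

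**Events as failures.** The only such rule is in the sensitivity paragraph of SAP 5.1: "patients who took any rescue medication prior to Week 8 will be considered as a treatment failure". SAP 1.3.2.2 describes rescue during treatment only as artificial tears supplied by the sponsor.

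**Sets and visits.** The FAS needs one dose; the FTS needs treatment through Visit 6 (SAP 2.6.3, 2.6.4). Early discontinuers complete the Visit 6 procedures (Protocol 6.2). SAP 2.5 ignores the protocol windows and assigns data to the nearest scheduled visit.

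**The concern.** An eye can be a deterioration under the protocol and a success under the SAP at the same visit: for example, central Grade 1 with a 12-letter loss or a new infection. An eye can also reach Grade 0 or 1 after prohibited topical therapy or a procedure, in which case the healing cannot be credited to the study product alone.

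The SAP accepts that added treatment can compromise the endpoint, since it fails patients who used rescue. But the rule reaches only a lubricant. Protocol 2.1 describes tarsorrhaphy and amniotic membrane transplantation as able to restore ocular integrity in advanced disease, and Protocol 2.4.1 lists suture-less membrane and contact lenses as alternatives. None of these is a failure in any analysis.

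The trial has one open-label arm, so the healing percentage is itself the result, and no control arm is affected in the same way.

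**Working it through.** **1. The plan's own precision.** Protocol 9.1 gives "A sample size of 35 evaluable patients" with assumed healing of "58% (at 4-week) and 72% (at 8-week), respectively", and a "lower limit of 95% confidence interval equal to 40% and 54" percent. SAP 5.4 specifies Clopper-Pearson intervals:

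- lower limit = Beta quantile(0.025; x, n − x + 1)
- upper limit = Beta quantile(0.975; x + 1, n − x)

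With n = 35, x = 0.58 × 35 = 20.3 gives 40.2%, and x = 0.72 × 35 = 25.2 gives 54.3%. Both stated limits are reproduced. They use fractional counts; the nearest whole count at Week 8, 25/35, gives 53.7%.

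**2. Which eyes can be both deteriorated and healed.**

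| Event in the study eye | Possible with central Grade 0 or 1? | Failure in any planned analysis? |
|---|---|---|
| Unchanged Grade 3 | No | Yes, on staining |
| PED, melt or perforation | Unlikely if central | Only through staining |
| Progression in other zones | Yes | Partly, through the secondary complete-healing endpoint |
| Loss of more than 10 letters | Yes | No |
| Infection | Yes | No |
| Need for ocular surgery | Yes | No |
| Prohibited topical therapy or a procedure | Yes | No |
| Artificial-tear rescue | Yes | Yes, in a sensitivity analysis only |

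LOCF and WOCF act only on missing Week 8 values, so they leave an observed Grade 0 or 1 untouched. SAP Appendix 2 lists LOCF and WOCF tables but no separate rescue table, so it is unclear whether the rescue rule is part of the WOCF run.

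**3. How such an eye reaches the Week 8 result.**

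- *Event found at the Week 8 visit:* the staining grade is observed and counts.
- *Prohibited treatment in a patient who stays in:* possible, because Protocol 6.2 says such patients can be discontinued, not that they must be. The grade counts.
- *Earlier exit:* if the exit exam keeps its Visit 6 label, it counts in the FAS. If SAP 2.5 reassigns it by date, exams before about Day 42, the midpoint (28 + 56)/2, go to Week 4. If the Day 42 pick-up visit counts as a scheduled visit, the boundary is Day 49, the midpoint (42 + 56)/2. The patient is then missing at Week 8, though LOCF can restore a healed grade. The FTS drops patients whose treatment stopped early.

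**4. Size, as illustration.** Assume 35 patients, 25 healed on staining, of whom k had such an event. The values of k are assumptions.

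| k | Healed | Rate | Exact 95% CI |
|---|---|---|---|
| 0 | 25/35 | 71.4% | 53.7 to 85.4 |
| 1 | 24/35 | 68.6% | 50.7 to 83.1 |
| 2 | 23/35 | 65.7% | 47.8 to 80.9 |
| 3 | 22/35 | 62.9% | 44.9 to 78.5 |

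Each patient moves the estimate by 1/35 = 2.9 points and the lower limit by about 3.

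The 35 are completers. Patients who stop before 8 weeks are replaced (Protocol 6.2), so the FAS is larger if any do. With two replaced patients, both at Grade 0 or 1 on an exit exam counted as Week 8, the FAS rate is 27/37 = 73.0% (55.9 to 86.2). Counted as not healed, it is 25/37 = 67.6% (50.2 to 82.0).

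**The case against.** The best reply is that the deterioration criteria are discontinuation rules, not efficacy definitions. The protocol defines epithelial healing by staining throughout; a 10-letter loss can have a non-epithelial cause; and folding vision, infection and surgery into an anatomical endpoint is a choice of estimand. Adverse events, discontinuation reasons, BCDVA change, concomitant medications and deviations are reported separately. The study is descriptive, with no hypothesis test.

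Much of this stands, and it is why the primary definition should not change. It does not answer the gap: those outputs are not linked to healing status, and the listed BCDVA tables cover change and 15-letter gain, with no count of eyes that lost more than 10 letters.

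The surgery route is also thin. Needing a procedure triggers the exit, so an operation would normally follow the last staining exam, and patients expected to need ocular surgery are excluded.

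Two stronger readings are tempting, and the documents do not support them:

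- *The bias can only favour the product.* Reclassifying healers can only lower the rate, by construction. But Protocol Table 3 also restricts drops that can induce corneal toxicity, and these could worsen staining. The direction of the effect of prohibited therapy is not known.
- *Some number of events takes the lower limit below the planned 54%.* With 25/35 and no events it is already 53.7%, and 54% is a precision figure, not a success threshold.

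**Conclusion.** The gap is real but limited. An eye with central Grade 0 or 1 at the assessment used for Week 8 is a primary success whatever else happened to it, and no planned analysis shows what the rate would be if prohibited treatment, a procedure, or the vision, infection or surgery criteria counted as failure. This is clearest for events found at Week 8 and for prohibited treatment in patients who remain. For earlier exits it depends on visit mapping, and the FTS limits it.

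A reader might infer that every deteriorated eye counts as healed, or that rescue is penalised in the main result. Neither is so: the staining grade must be 0 or 1, and rescue is not a failure in the primary analysis either.

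The size is unknown because the documents give no event rates. At about 3 points per patient, even one or two would be visible in a sample this small. The consequence is for the interpretation of an estimate, not for type I error. The change is worth making because it is cheap and extends logic that the SAP already uses.

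**What to change.** In SAP 5.1, extend the rescue-as-failure rule with one FAS sensitivity analysis. Besides rescue users, it counts as not healed any patient who, at or before the Week 8 assessment, either:

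- received prohibited topical ocular therapy or an ocular procedure in the study eye, or
- met a vision, PED/melt, infection or surgery criterion of Protocol 3.3 in that eye.

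Show the rate and exact interval beside the staining-only rate, with the number of patients reclassified for each reason. For vision, the SAP's own conversion (15 letters = 0.3 logMAR, so 0.02 per letter) makes a loss of more than 10 letters a logMAR increase above 0.2. State also whether the rescue rule belongs to the WOCF run or stands alone, and whether a discontinuation exam keeps its Visit 6 label under SAP 2.5.

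Leave the primary definition and the discontinuation rules unchanged.

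Cost: one paragraph and one table, from BCDVA, adverse events, concomitant medications, deviations and termination reasons, all already collected. The supportive rate may come out lower. If no such events occur, the table shows that the result does not depend on them.
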